8.2.1.3 Adverse Events by Baseline Characteristics

The following will be presented for AEs, split by the baseline characteristics using the safety analysis set:

- The number of subjects to whom AE occurred and the number of AEs will be calculated.
- The proportion of subjects to whom AE occurred and its 95% confidence interval will be estimated and compared between subcategories of each baseline characteristic using chi-square test or Fisher's exact test.
- Adverse event presentations will be split by the following baseline characteristics:
 - Age (< 30 years, \geq 30 years and \leq 49 years, \geq 50 years and \leq 69 years, \geq 70 years)
 - Geriatric status (<65 years, \geq 65 years)
 - Sex (Male, Female)
 - Pregnancy (Yes, No)
 - Breast-feeding (Yes, No)
 - Duration of disease (<3 months, \geq 3 months and <6 months, \geq 6 months)
 - Severity of disease (Mild, Moderate, Severe)
 - Medical History (Past Disease, Present Disease/Yes, No)
 - Allergic history (Yes, No)
 - Recent past psychotropic medication (Yes, No)
 - Total administration period of PRISTIQ® (< 4 weeks, \geq 4 weeks and <8 weeks, \geq 8 weeks and <12 weeks, \geq 12 weeks)
 - Mean daily dose of PRISTIQ® excluding days of missed doses (<50 mg/day, \geq 50 mg/day and <100 mg/day, \geq 100 mg/day and \leq 200 mg/day)
 - Renal disorder (Yes, No)
 - Hepatic disorder (Yes, No)

- Long-term administration (<6 months (180 days), \geq 6 months (180 days) of total administration period of PRISTIQ®)
- Concomitant medication (Yes, No)

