7.4.10.3. Adverse events data collection

The investigator collects data on safety events as specified in Section 9 including all adverse events that occur during the observation period regardless of causal relationship to PRISTIQ®. The information on adverse events should include the specific conditions or events, duration of the events (start date and stop date), seriousness (serious or non-serious), severity, causal relationship to PRISTIQ®, actions taken, and outcome.

Check either 'yes' or 'no' in adverse event occurrence section. If 'yes', record in detail.

- Adverse event: Record the term of adverse event. If possible, specify diagnosis, not individual symptoms.
- Date of onset: Record the date of onset.
- Severity: Severity evaluation of adverse events must be done according to the following category.

1. Mild- Not causing any significant problem to the subject; Continuous medication of study drug is possible without dose adjustment.
2. Moderate- Cause a problem that does not interfere significantly with usual activities or the clinical status; Dose adjustment of study drug or other therapy is needed due to adverse event.
3. Severe- Cause a problem that interferes significantly with usual activities or the clinical status; Study drug should be stopped due to adverse event.

If the severity of an adverse event changed, the adverse event must be entered separately. Record stop date of previous severity and onset date of new severity – along with completion of all other items.

- Action: Check all relevant actions.

1) PRISTIQ®: Check the appropriate number for the adjustment of PRISTIQ® resulted from the adverse event.

1. Withdrawn (temporarily or permanently, or delayed)
2. Dose reduced
3. Dose increased
4. Dose not changed
5. Unknown
6. Not applicable

2) Others: After the onset of adverse event, the investigator should indicate other actions taken and record in detail.

1. Treatment given (please specify in concomitant medication section)
2. Others (please specify)
3. No action taken

- Seriousness: Check either ‘yes’ or ‘no’ for the question, ‘Is this case under the criteria of serious adverse event?’ If ‘yes’, record the appropriate number for the category of seriousness.

A serious adverse event is any untoward medical occurrence at any dose that:

- results in death;

- is life-threatening;
- requires inpatient hospitalization or prolongation of hospitalization;

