7.7. Data Analysis

The data collected in this study will be documented in a Statistical Analysis Plan, which will be maintained by the sponsor. This document may modify the plans outlined in the protocol; however, any major modifications of primary endpoint definitions or their analyses will be reflected in a protocol amendment.

No formal sample size calculations were performed for this study. Six hundred (600 patients) or more will be collected as per the requirement by MFDS. Safety summaries will be based on the safety analysis set defined as those patients who met inclusion / exclusion criteria and completed safety follow-up. Effectiveness summaries will be based on the effectiveness analysis set, defined as those patients who took at least 8 weeks of PRISTIQ® and completed effectiveness evaluation.

In addition, special subject groups -elderly group (more than or equal to 65 years old), hepatic disorder group, renal disorder group and pregnancy group- will be analyzed separately.

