7.7.1. Safety analysis

- Count and frequency of occurrence of adverse event, serious adverse event, adverse drug reaction or unexpected adverse event by category.
- Count and frequency of occurrence of adverse events by subject baseline factor and by treatment factor to determine factors affecting the safety.
- If there is any particular pattern in abnormal findings (including clinical laboratory abnormalities) occurring during or after the treatment which were considered unrelated to PRISTIQ®, the count and frequency of the events will be tabulated and analyzed to determine the causal relationship to the relevant study drug.

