7.7.3. Statistical consideration

The significance of the difference between sub-categories with regard to safety and effectiveness will be statistically analyzed using χ^2 test ($p \leq 0.05$), etc. The frequency of occurrence of each adverse event will be presented with its 95% confidence interval.

To determine factors affecting the safety, the count and frequency of occurrence of all adverse events will be tabulated by type of the event and subject's baseline factor (gender, age, presence of concurrent disease, etc.), and factors considered potentially affecting the safety will be analyzed using categorical data analysis method (Chi-square test, Fisher's Exact test), etc. Serious adverse events, adverse drug reaction and unexpected adverse events, etc. will be also tabulated and summarized.

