8.2 STATISTICAL ANALYSES

8.2.1 Safety Analyses

8.2.1.1 Demographic and Baseline Characteristics

Baseline characteristics for this study are defined as follows:

- Continuous measurements:
 - Age
 - Duration of disease[†]
 - Total administration period of PRISTIQ^{®‡}
 - Total dose of PRISTIQ^{®¶}

- Mean daily dose of PRISTIQ® excluding days of missed doses[§]
- Categorized measurements:
 - Age (< 30 years, \geq 30 years and \leq 49 years, \geq 50 years and \leq 69 years, \geq 70 years^{*})
 - Geriatric status (<65 years, \geq 65 years)
 - Sex (Male, Female)
 - Pregnancy (Yes, No)
 - Breast-feeding (Yes, No)
 - Duration of disease[†] (<3 months, \geq 3 months and <6 months, \geq 6 months^{*})
 - Severity of disease (Mild, Moderate, Severe)
 - Medical History (Past Disease, Present Disease/Yes, No)
 - Allergic history (Yes, No)
 - Recent past psychotropic medication (Yes, No)
 - Total administration period of PRISTIQ^{®‡} (< 4 weeks, \geq 4 weeks and <8 weeks, \geq 8 weeks and <12 weeks, \geq 12 weeks^{*})
 - Mean daily dose of PRISTIQ® excluding days of missed doses (<50 mg/day, \geq 50 mg/day and <100 mg/day, \geq 100 mg/day and \leq 200 mg/day^{*})
 - Renal disorder (Yes, No)
 - Hepatic disorder (Yes, No)
 - Long-term administration (<6 months (180 days), \geq 6 months (180 days) of total administration period of PRISTIQ®)
 - Concomitant medication (Yes, No)

[†] Duration of disease = First start date of PRISTIQ® – Diagnosis Date + 1

Subjects whose diagnosis date is included 'Unknown' are excluded from the analysis
(Footnote will be added to the relevant outputs to indicate the number of subjects collected 'Unknown')

[‡] Total administration period of PRISTIQ® = Sum of each period of administration

- In safety analysis set

Sum of each period of administration = (Last administration end date) – (First administration start date) + 1

If the medication is being continued at the completion of the study, last administration end date is replaced with last date collected in data.
- In effectiveness analysis set
 - If final effectiveness evaluation is evaluated after last administration end date,

Sum of each period of administration = (Last administration end date) – (First administration start date) + 1
 - If final effectiveness evaluation is evaluated before last administration end date or the medication is being continued at the completion of the study,

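### Treatment duration is fixed only after treatment but tested as a baseline characteristic, so its two p-values for adverse events cannot be read as an effect of duration

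*SAP*

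**What the plan says.** SAP 8.2.1.3 states: "The proportion of subjects to whom AE occurred and its 95% confidence interval will be estimated and compared between subcategories of each baseline characteristic", by chi-square or Fisher's exact test. SAP 8.1 sets the level at two-sided 0.05. Two of the listed characteristics are "Total administration period of PRISTIQ® (< 4 weeks" and so on, with further cuts at 8 and 12 weeks, and "Long-term administration (<6 months (180 days" against 180 days or more.

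SAP 8.2.1.1 puts both under its baseline characteristics. In the safety set it computes the period from first start date to last end date. If treatment is continuing, "last administration end date is replaced with last date collected in data".

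Protocol 7.7.1 asks for AE counts "by subject baseline factor and by treatment factor to determine factors affecting the safety", so it names the two kinds of factor separately. Protocol 7.7.3 opens with a general provision for chi-square tests between sub-categories. It then refers to "baseline factor (gender, age, presence of concurrent disease, etc.), and factors considered potentially affecting the safety will be analyzed using categorical data analysis method". One of the actions recorded for an AE in protocol 7.4.10.3 is "Withdrawn (temporarily or permanently, or delayed").

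**The concern.** A baseline characteristic is known before any AE can occur. Duration is not, and two mechanisms tie it to the outcome even if it has no effect on AEs.

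- **Reverse causation.** An AE that ends treatment shortens the administration period and so chooses the subject's stratum. (A temporary interruption need not, because the period runs from first to last date.)
- **Unequal time at risk.** A subject observed for longer has more time to record a first AE, and the observation period can depend on how long the drug was taken.

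The stated purpose of the splits is to find factors that affect safety. A small p-value here could lead the re-examination report to name duration as such a factor when the difference comes from how the strata are formed.

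**Working it through.** The plan has no figure to reproduce: 600 is a regulatory number and protocol 7.7 says no sample size calculation was made. The check is whether the two tests hold their 0.05 level when duration has no effect.

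**Inputs from the documents.** 600 subjects; at least 60 treated over 6 months (protocol 7.3.3.1), i.e. 60/600 = 10%; strata cut at 4, 8 and 12 weeks and at 180 days; two-sided 0.05.

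**Assumed mid-case.** AE by week 8, *a* = 20%; background stopping by week 8, *b* = 25%; share of AEs that stop the drug, *s* = 30%; 10% reach 180 days; same constant AE hazard for all.

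**Reverse causation alone** (everyone observed for the same 8 weeks):
- On drug at week 8: (1 − b)(1 − a·s) = 0.75 × 0.94 = 0.705, or 423 of 600.
- With an AE among them: a(1 − s)/(1 − a·s) = 0.14/0.94 = 14.9%.
- With an AE among the other 177: (0.200 − 0.705 × 0.149)/0.295 = 32%.

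So 32% against 15% arises with an identical hazard.

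**Time at risk alone** (*s* = 0). The proportion with an AE in *d* days is 1 − 0.8^(d/56):
- stopped on day 14, observed to day 42: 15.4%
- observed to week 8: 20%
- observed to day 84: 28.4%
- treated 180 days, observed to day 208: 56.3%

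**Both mechanisms, by simulation** (mid-case; exponential times; stopping after week 8 set so that 10% reach 180 days; cap 52 weeks). The documents do not fix one AE window for subjects treated past week 8, so four readings were run.

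| AE window | % with AE: <4 / 4–<8 / 8–<12 / ≥12 wk | Four-category test rejects | % with AE: <180 / ≥180 d | 180-day test rejects |
|---|---|---|---|---|
| Protocol 7.1: week 8, or last dose + 28 d if stopped earlier | 30/34/14/15 | 98% | 20/17 | 9% |
| Literal protocol 9.2: 28 d beyond week 8 if still on drug | 30/34/28/22 | about 53% | 27/24 | 6–7% |
| Last dose + 28 d for all | 30/34/31/45 | 82% | 35/59 | 94–95% |
| Mixed: 7.1, but last dose + 28 d for those reaching 180 d | 30/34/14/25 | 92% | 20/59 | 100% |

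With no AE-related stopping, the four-category test still rejects about 19%, 55–57% and 100% under the first three windows. With an equal 8-week window and no AE-related stopping, both tests reject 4–6%, so the simulation is calibrated.

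**Range over 36 settings** (a = 10, 20, 30%; s = 0, 10, 30, 50%; b = 15, 25, 40%):
- Four-category test: under 7.1, 7–42% with no AE-related stopping and 17–100% with it; about 8–100% under literal 9.2; 21–100% with collection to last dose + 28 d for all; 33–100% mixed.
- 180-day test: under 7.1, 4–9% for *s* up to 30% and 15–25% at 50%; under literal 9.2, about 4–15% and 13–30%; 34–100% with collection to last dose + 28 d for all; 95–100% mixed.

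**The case against.** **The protocol foresees these tables.** Section 7.7.1 names treatment factors, and the first sentence of 7.7.3 provides for chi-square tests between sub-categories without restricting them to baseline factors. The examples given later in 7.7.3 are all fixed before treatment, but the list is open-ended. This stands. A reader might infer that the SAP departs from the protocol, and the documents do not support that. The faults are the baseline label and the test.

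**The 180-day test may be nearly sound.** This stands in part. Under the 7.1 and literal 9.2 windows its error rate stays fairly close to 5% unless about half of AEs stop the drug. A reader might infer that both p-values are badly inflated. For the 180-day test that requires AE collection to last dose in long-term users. Protocol 7.3.3.1 and 9.2 point past week 8, while 7.1, 7.3.3 and 7.4.10.3 tie collection to a period ending at week 8.

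**Little depends on the result.** SAP section 4 sets no hypotheses, and protocol 7.9 concedes limitations of the uncontrolled design. That lowers the severity. It does not make the p-values interpretable, and nothing in the SAP marks them as descriptive.

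**Two other rows share the problem.** Mean daily dose and concomitant medication are also set after the first dose, and protocol 7.4.6 lists treatment of an AE among the purposes of concomitant medication. This is correct and is taken up in the fix.

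**Conclusion.** The concern holds for the label and for the two p-values. The counts, proportions, confidence intervals and listing of long-term subjects are not at fault.

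The four-category test is unreliable under every window examined: about 53–98% rejection in the mid-case with no true effect, and well above 5% in most other settings. The 180-day test is at about 6–9% in the mid-case under the two shorter windows and about 95–100% if long-term users have AEs collected to last dose. Its direction also changes with the window (20% against 17%, or 35% against 59%), so neither its size nor its sign can be read as a duration effect.

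The sizes rest on assumed AE and stopping rates. The conclusion that the p-values are not interpretable does not, because both mechanisms follow from how the strata are defined. Severity is low to moderate: the possible harm is a wrong statement in the re-examination report.

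**What to change.** 1. In SAP 8.2.1.3, list total administration period and long-term administration as treatment factors. Keep counts, proportions and 95% confidence intervals, and drop their two p-values.
2. Add a footnote: *Strata are defined after treatment start, can be changed by the AE itself and differ in time at risk; they do not show an effect of duration.*
3. State that this modifies the testing in protocol 7.7.3. Protocol 7.7 allows it: "This document may modify the plans outlined in the protocol". No endpoint definition changes.
4. SAP 8.2.2 takes its effectiveness subgroups by cross-reference from 8.2.1.3. Write that list out there so that it is not changed by accident.
5. Reconcile protocol 7.1, 7.3.3, 7.3.3.1, 7.4.10.3 and 9.2 on the AE window for subjects treated past week 8, and report which window was applied.
6. Mean daily dose and concomitant medication can take the same label and footnote.

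A descriptive table of first-AE rates per person-time by time since first dose is optional and not part of the required change.

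The cost is SAP wording and the loss of a formal test of duration.

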7.4.5. Administration status for PRISTIQ®

Record the followings with regard to administration status for the study drug. If the posology is changed (including wash-out), please record in a separate row and the reason.

- Treatment start date
- Treatment stop date
- Daily dosage and frequency
- Reason for dose adjustment: Select one among 'planned dose increase or decrease', 'cure or improvement', 'occurrence of adverse event', 'withdrawal due to lack of efficacy' or 'other'. If 'other', record the specific reason.

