Sum of each period of administration = (Date of final effectiveness evaluation) – (First administration start date) + 1

[¶] Total dose of PRISTIQ® = Sum of each dose of administration

: Each dose of administration = (Administration end date - Administration start date +1)*(Total daily dose)

§ Mean daily dose of PRISTIQ® excluding days of missed doses = Total dose of PRISTIQ® / Total administration period of PRISTIQ® excluding days of missed doses

* The above categories can be altered depending on the data distribution.

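### The only dose split for adverse events uses whole-course mean daily dose, which the event itself can lower, so the comparison is diluted and can be biased against the higher dose

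*SAP*

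**What the plan says.** SAP 8.2.1.3 lists the characteristics by which adverse events are split. The only one that measures dose is "Mean daily dose of PRISTIQ® excluding days of missed doses (<50 mg/day, \geq 50 mg/day and <100 mg/day, \geq 100 mg/day and \leq 200 mg/day". The proportion of subjects with an event is to be "compared between subcategories of each baseline characteristic using chi-square test or Fisher's exact test", two-sided at 0.05 (SAP 8.1).

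SAP 8.2.1.1 defines mean daily dose as "Total dose of PRISTIQ® / Total administration period of PRISTIQ® excluding days of missed doses". The numerator sums the dosing rows: "Each dose of administration = (Administration end date - Administration start date +1)*(Total daily dose". In the safety set, administration runs to the last administration date, or to the last date collected if treatment continues. Nothing truncates it at the event. A footnote adds: "The above categories can be altered depending on the data distribution".

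The protocol collects the dose history. Section 7.4.5 says "If the posology is changed (including wash-out), please record in a separate row and the reason", with start and stop dates for treatment. Planned dose changes and adverse events are both among the coded reasons for adjustment. Section 7.4.10.3 records the onset date of each event and, under action taken, says "Check the appropriate number for the adjustment of PRISTIQ® resulted from the adverse event". Dose reduction is one of the coded answers. Protocol 7.7.1 states the purpose: frequencies by baseline and treatment factor, to find factors that affect safety.

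**The concern.** Mean daily dose is not a baseline characteristic. It is known only after treatment, and an adverse event can change it. When an event at 100 mg leads to a cut to 50 mg, the subject and the event leave the upper band because the event happened. That removes events selectively from the higher-dose group and adds them to the lower one.

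A second, milder fault is that the middle band mixes subjects always on 50 mg with all those raised from 50 to 100 mg, so events that arise at 100 mg after titration count in the lower band.

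At stake is the one table, with a p-value, from which a reader of the re-examination report would judge whether adverse events relate to dose. No other planned analysis uses starting dose, maximum dose or dose at onset. Altering the band limits, as the footnote allows, leaves the metric a whole-course mean.

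**Working it through.** The plan has no figure of its own to reproduce: protocol 7.7 says no formal sample size calculation was made, and neither document gives event rates or shares of dose changes.

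**Step 1. Dose paths through the SAP formula (no assumption about rates).** Take 56 days, the 8-week observation period. Dose levels are used only as arithmetic on the SAP's band limits. Mean = (d × first dose + (56 − d) × second dose) / 56.

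| Path | Switch after day d | Mean, mg/day | Band |
|---|---|---|---|
| 50 to 100 | 1 | (50 + 5,500)/56 = 99.1 | 50 to <100 |
| 50 to 100 | 28 | (1,400 + 2,800)/56 = 75.0 | 50 to <100 |
| 50 to 100 | 55 | (2,750 + 100)/56 = 50.9 | 50 to <100 |
| 100 to 50 | 1 | (100 + 2,750)/56 = 50.9 | 50 to <100 |
| 100 to 50 | 55 | (5,500 + 50)/56 = 99.1 | 50 to <100 |
| 100, then stop | any | 100 | 100 to 200 |
| 100 to 25 | 14 | (1,400 + 1,050)/56 = 43.75 | <50 |
| 50 to 200 | 7 | (350 + 9,800)/56 = 181.25 | 100 to 200 |
| 50 to 200 | 42 | (2,100 + 2,800)/56 = 87.5 | 50 to <100 |

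Every path between 50 and 100 mg lands in the middle band. The last four rows show paths for which that rule does not extend to a stop, to a cut below 50 mg or to doses above 100 mg.

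**Step 2. Effect on the comparison (assumed inputs).** Assume 15% start on 100 mg; 35% of the rest go from 50 to 100 mg between days 7 and 28 (about 17.5 days on average); the daily hazard of a first event is 0.004 on 50 mg and either 0.008 (true doubling) or 0.004 (no effect) on 100 mg; and a share c of events on 100 mg leads to a cut to 50 mg.

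Proportions with an event by day 56:
- Always 50 mg: 1 − 0.996^56 = 20.1%.
- Start on 100 mg, doubling: p = 1 − 0.992^56 = 36.2%. No effect: p = 20.1%.
- Titrated, doubling: 1 − 0.996^17.5 × 0.992^38.5 = 31.6%.
- All who start on 50 mg, doubling: q = 0.65 × 20.1 + 0.35 × 31.6 = 24.1%. No effect: q = 20.1%.

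With cuts, the bands show:
- Upper band: p(1 − c) / (1 − pc).
- Middle band: (0.85q + 0.15pc) / (0.85 + 0.15pc).

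For a doubling and c = 0.6, the upper band is 0.362 × 0.4 / (1 − 0.217) = 18.5%, and the middle band is (0.205 + 0.033) / (0.85 + 0.033) = 26.9%.

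A simulation of 600 subjects (500 runs, chi-square at 0.05, 20% stopping after an event) agrees with these formulas:

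| Truth | c | Middle vs upper, formula | Middle vs upper, simulated | Significant |
|---|---|---|---|---|
| Doubling | 0 | 24.1% vs 36.2% | 23.9% vs 36.2% | right direction 68% |
| Doubling | 0.3 | 25.5% vs 28.4% | 25.5% vs 28.9% | right direction 10% |
| Doubling | 0.6 | 26.9% vs 18.5% | 27.0% vs 18.3% | wrong direction 32% |
| No effect | 0.6 | 21.8% vs 9.1% | 21.7% vs 9.3% | false protective 79% |

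The contrast is zero when the upper band equals the overall proportion, 0.85 × 24.1 + 0.15 × 36.2 = 25.9%. That gives c = (0.362 − 0.259) / (0.362 × 0.741) = 0.38. So under these inputs a true doubling is hidden when about 38% of events on 100 mg lead to a cut.

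**Step 3. Starting dose under the same inputs.** Cuts cannot move a subject between starting-dose groups, so the split is q vs p whatever c is: 24.1% vs 36.2% with a doubling and 20.1% vs 20.1% with no effect.

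**Step 4. Dose at onset.** First events per person-day at the dose in force gave about 4.0 vs 8.0 per 1,000 days with a doubling, and were significant in 98 to 99% of runs, when the hazard was constant over time. With a front-loaded hazard (2.5 times base in days 1 to 14 and 0.5 times after, assumed) and no dose effect, the crude rates were about 4.8 vs 2.9 per 1,000 days. That is a false protective result, because titrated subjects spend their early days on 50 mg.

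**The case against.** The strongest case against has four parts.

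- **The damage depends on an unknown.** Vanishing or reversal needs frequent event-driven cuts. The documents give no such share, and protocol 7.4.10.3 describes mild events as needing no dose adjustment. With no cuts the bands keep the right direction. This stands, and it limits the claim: pooling titrated subjects alone only dilutes.
- **The setting is descriptive.** SAP 4 marks hypotheses and decision rules as not applicable, protocol 7.9 admits the limits of an uncontrolled design, and dose is one of many exploratory splits. This lowers the stakes but does not remove the point, because protocol 7.7.1 wants factors affecting safety and the SAP attaches a test.
- **The distortion is partly visible.** SAP 8.2.1.4 tabulates events by action taken, so the number of dose reductions can be read off. That warns a careful reader but gives no dose at onset and no denominator by dose.
- **Dose at onset is no simple cure.** Crude rates confound dose with time on drug. SAP 8.2.1.2 also expects partial onset dates, SAP Appendix 1 drops ambiguous daily dosages, and protocol 9.2 includes at least 28 days after the last administration, when no dose is in force. This stands.

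A reader might also infer that every subject reduced from 100 mg after an event moves to the middle band, or that the upper band holds only subjects never below 100 mg. The paths in the working show otherwise: a stop from 100 mg stays in the upper band, an early cut below 50 mg can fall in the lowest, and 50 then 200 mg can average well above 100.

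**Conclusion.** The point holds in a bounded form. SAP 8.2.1.3 tests adverse events against a post-baseline dose measure that it labels as baseline and that the event itself can lower. The placement of all 50-to-100 and 100-to-50 mg paths in the middle band is exact arithmetic. The direction of the bias is also clear: event-driven cuts move events out of the upper band.

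The size is not known. Under the assumed rates and titration share, a true doubling shows as anything from a diluted 24% vs 36% (no cuts) to a reversed 27% vs 18% (60% cut), and no effect can appear as 22% vs 9%. The documents therefore do not support saying that a dose effect will vanish, only that it can be hidden, or a false protective one produced, if cuts are frequent. This is a change the plan should make. It takes no view on dosing.

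**What to change.** In SAP 8.2.1.3:

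1. Make the tested dose split the proportion of subjects with an adverse event by starting daily dose, taken from the first dosing row of protocol 7.4.5.
2. Keep mean daily dose as a descriptive exposure summary without a test, with a footnote that it is measured after baseline and can be altered by the event.
3. Optionally add first adverse events by dose in force at onset, per person-days at that dose, stratified by or adjusted for time since first dose (for example weeks 1-2, 3-4 and 5-8). State the rule for partial onset dates, ambiguous daily doses and events after the last dose.

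Cost: SAP wording and one or two more tables, with no new data. Item 3 also needs a derived dataset that joins onset dates to dosing rows. Downsides: cells at higher starting doses may be small, and a starting-dose split does not capture the effect of later titration.

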7.4.6. Concomitant medications

Record the medicated drug while PRISTIQ® is being administrated. First select either 'yes' or 'no' then record in more details if selected 'yes'.

- Name of medication (generic name)

- Treatment start date
- Treatment stop date
- Ongoing: If the treatment is not terminated until the timing of CRF completion, check 'ongoing'.
- Purpose of treatment: Select one among 'treatment for major depressive disorder', 'treatment for other diseases', 'treatment for an adverse event', 'prevention of drug side effect', or 'other'. If 'other', record the specific reason.

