8.2.2 Effectiveness Analyses

Statistical analysis on effectiveness parameter after 8 weeks treatment of PRISTIQ® will be done on effectiveness analysis set.

For collected data separately,

- The overall improvement rate (the proportion of patients considered “Improved”) will be estimated with its 95% confidence interval.
- Frequency and percentage of results for Final Effectiveness (‘Improved’, ‘No change’, ‘Worse’) will be summarized.

The improvement rate according to the baseline characteristics listed in section 8.2.1.3 will be analyzed. Chi-square test or Fisher’s exact test will be used for comparing between subcategories of each baseline characteristic

Additionally, the distribution of subjects according to the CGI-I scale (‘1. Very much improved’, ‘2. Much improved’, ‘3. Minimally improved’, ‘4. No change’, ‘5. Minimally worse’, ‘6. Much worse’, ‘7. Very much worse’) at last visit will be summarized.

Following statistical analysis on effectiveness parameter after 6 months(180 days) treatment of PRISTIQ® will be done on long-term effectiveness analysis set.

- Frequency and percentage of results for Final Effectiveness (‘Improved’, ‘No change’, ‘Worse’) will be summarized.
- Distribution of subjects according to the CGI-I scale (‘1. Very much improved’, ‘2. Much improved’, ‘3. Minimally improved’, ‘4. No change’, ‘5. Minimally worse’, ‘6. Much worse’, ‘7. Very much worse’) at last visit will be summarized.

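### Concomitant medication is tested as a baseline factor for adverse events, yet a drug given to treat an adverse event also makes the subject a Yes

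*SAP*

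**What the plan says.** SAP 8.2.1.1 opens its list with "Baseline characteristics for this study are defined as follows" and includes concomitant medication as a Yes/No item. SAP 8.2.1.3 repeats the item as "Concomitant medication (Yes, No" and says the proportion of subjects with an AE will be "compared between subcategories of each baseline characteristic using chi-square test or Fisher's exact test". The SAP footnotes derivations for duration of disease, administration period, total dose and mean daily dose. It gives none for concomitant medication.

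The source of the variable is Protocol 7.4.6: "Record the medicated drug while PRISTIQ® is being administrated". One yes/no item covers every purpose, and the listed purposes include "treatment for an adverse event', 'prevention of drug side effect". Start and stop dates are also recorded. In Protocol 7.4.10.3, an action the investigator can tick for an AE is "Treatment given (please specify in concomitant medication section".

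Protocol 7.7.1 gives the purpose of the split: AEs are tabulated "by subject baseline factor and by treatment factor to determine factors affecting the safety". SAP 8.2.2 reuses the list for effectiveness: "The improvement rate according to the baseline characteristics listed in section 8.2.1.3 will be analyzed".

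**The concern.** A baseline factor should be fixed before the outcome can occur. This one is not. It is collected over the on-treatment period in which AEs are counted, and an AE can itself switch it from No to Yes. When that happens, one subject with an AE leaves the No group and joins the Yes group. This mechanism can only raise the AE proportion in Yes and lower it in No.

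The affected table is the one meant to identify factors that influence safety, and it feeds the regulatory reports. It could present use of other drugs as such a factor when part or all of the difference comes from how the variable is recorded.

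The problem is limited to subjects with no other drug whose AE is drug-treated while PRISTIQ continues. A drug begun after PRISTIQ is stopped may fall outside Protocol 7.4.6.

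**Working it through.** The plan states no rate, power or effect size for this comparison, so there is no figure of its own to reproduce.

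**Inputs from the documents.** N = 600 (Protocol 7.2 and 7.7). Two-sided 0.05 (SAP 8.1). Chi-square test, or Fisher's exact test when more than 20% of cells have an expected count below 5 (SAP 8.1.2).

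**Assumed inputs.** p = AE risk per subject; c = share on another drug at first dose; t = share of AE subjects given a drug for the AE while on PRISTIQ. Background use is taken as independent of AEs, so there is no true association.

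**Cell probabilities under the plan.**
- AE and Yes: p[c + (1 − c)t]
- AE and No: p(1 − c)(1 − t)
- No AE and Yes: (1 − p)c
- No AE and No: (1 − p)(1 − c)

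The spurious odds ratio is [c + (1 − c)t] / [c(1 − t)], which does not depend on p. The number of subjects moved is N·p·(1 − c)·t.

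**Worked case: p = 0.20, c = 0.70, t = 0.30.**
- AE and Yes = 0.20 × (0.70 + 0.30 × 0.30) = 0.158
- AE and No = 0.20 × 0.30 × 0.70 = 0.042
- No AE and Yes = 0.80 × 0.70 = 0.560
- No AE and No = 0.80 × 0.30 = 0.240
- AE risk in Yes = 0.158 / 0.718 = 22.0%; in No = 0.042 / 0.282 = 14.9%
- Odds ratio = 0.79 / 0.49 = 1.61
- Subjects moved = 600 × 0.20 × 0.30 × 0.30 = 10.8

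**Range.** Rejection rates come from 10,000 simulated trials per row under the SAP's test rule. N = 500 allows for exclusions from the safety set.

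| p / c / t | AE in Yes | AE in No | Moved (N = 600) | Rejects, N = 600 | Rejects, N = 500 |
|---|---|---|---|---|---|
| 20% / 90% / 10% | 20.2% | 18.4% | 1 | 5% | 5% |
| 20% / 90% / 30% | 20.5% | 14.9% | 4 | 15% | 12% |
| 20% / 80% / 30% | 21.2% | 14.9% | 7 | 31% | 27% |
| 20% / 70% / 10% | 20.7% | 18.4% | 4 | 9% | 8% |
| 20% / 70% / 30% | 22.0% | 14.9% | 11 | 50% | 44% |
| 20% / 50% / 30% | 24.5% | 14.9% | 18 | 84% | 77% |
| 25% / 50% / 40% | 31.8% | 16.7% | 30 | 99% | 98% |

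With t = 0 and N = 600, rejection is 5.1% (c = 0.9) and 4.9% (c = 0.5), so the excess comes from the recording of AE treatment alone.

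**After redefinition.** With Yes restricted to drugs ongoing at first dose, 4,000 subject-level trials at N = 600 gave 4.8% to 5.6% in every scenario rerun (20/70/30: 50.7% as planned, 4.9% redefined). With a further 20% of non-users starting another drug later, independently of AEs, the 20/70/30 case gave 39.9% as planned, 5.5% with the first-dose definition and 5.4% when only AE-treatment drugs were excluded. The return to about 5% follows from assuming baseline use independent of AEs. It shows that the new definition adds no bias of its own, not that real data would be free of confounding.

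**The case against.** **The derivation is inferred.** The SAP never says in words how Yes is built. That is true, but the CRF has a single yes/no item and the SAP sets no filter, so following the plan as written counts AE drugs.

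**Treatment factors are allowed.** Protocol 7.7.1 plans splits by treatment factor as well as baseline factor, so an on-treatment variable is legitimate in itself. Relabelling it would still leave the exposure partly defined by the outcome.

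**The size is unknown.** This stands. Yes covers drugs for any purpose, so background use could be high, and at 90% rejection is about 5% or 15% in the cases above.

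**An opposing bias exists.** Subjects who stop PRISTIQ for an AE have less time to start other drugs, which pushes AEs towards No. Suppose p = 20%, c = 70%, t = 10%, and 20% of non-users without an AE start a drug later, against 10% of those with one. Yes is then 0.70 + 0.30 × (1 − 0.9 × 0.9) = 75.7% of AE subjects and 0.70 + 0.30 × 0.20 = 76.0% of the others, so the net bias is almost nil. At t = 30% it remains (81.1% against 76.0%). This is a second post-baseline distortion, and the cancellation is accidental. Excluding AE-treatment drugs alone would leave it: 73.0% of AE subjects would be Yes against 76.0% of the others. The first-dose definition removes both (70% in each).

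**It is one exploratory row.** SAP section 4 sets no hypotheses, and this is one of 16 unadjusted splits. If they were independent, the chance of at least one false positive would already be 1 − 0.95^16 = 56%. SAP 8.2.1.4 also tabulates AEs by other action, so readers can see how many were treated. These points limit the harm but do not correct the split.

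**Conclusion.** The concern holds. The documents establish the mechanism without any assumption about rates: a variable recorded on treatment, which AE treatment can turn to Yes, is tested as a baseline factor for AEs.

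The size cannot be fixed from the documents. Under the assumptions shown, it is negligible when nearly all subjects already take other drugs and few AEs are drug-treated. It is large (rejection of 50% to 84% at N = 600) when background use is 50% to 70% and about 30% of AE subjects are treated.

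Overall AE incidence and the serious AE, adverse drug reaction and unexpected AE tables are untouched. The change should be made, but it does not threaten the study's main outputs. Confidence is high for the mechanism and conditional for the magnitude.

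**What to change.** In SAP 8.2.1.1 and 8.2.1.3, define concomitant medication = Yes as at least one drug started on or before the first PRISTIQ dose and still ongoing at that dose. Add a short rule for two edge cases: a drug started on the day of first dose to treat an AE (which should not count), and unknown or partial start dates. Carry the same definition into SAP 8.2.2 so that the shared list has one meaning; no bias in the improvement rate is claimed here. Summarise drugs started later by purpose, descriptively and without a test.

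The cost is one SAP definition and a filter on fields already on the CRF, with no new data. The downside is that genuine combinations begun after the first dose leave the tested Yes group. If 20% of non-users start another drug later, that is 600 × 0.30 × 0.20 = 36 subjects at 70% background use, or 600 × 0.50 × 0.20 = 60 at 50%.

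If the sponsor wants those exposures kept in the test, the minimum change is to exclude drugs whose recorded purpose is AE treatment. This removes the circularity but leaves the variable post-baseline.
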